Hybrid pilot trial assessing efficacy as well as feasibility and acceptability

STUDY SITE

The study site for participant enrollment is the Gugulethu Midwife Obstetric Unit (MOU), based at the Gugulethu Community Health Centre near Cape Town, South Africa. The MOU serves Gugulethu as well as the surrounding informal settlements, and is often attended by women who come from the Eastern Cape to have their babies in Cape Town, resulting in travel to and from the Eastern Cape during pregnancy and postpartum.⁴¹ The local antenatal HIV prevalence is high (~30%), and the mother-to-child HIV transmission rate is estimated at 2-4%.⁴² The MOU team has helped to deliver HIV care and treatment services in this setting since 2003 and has a history of successful ART service delivery and research in partnership with the provincial government. [name] and [name] have conducted studies at the MOU since 2006.⁴³

ABOUT CARECONEKTA

CareConekta, developed in parallel with a series of focus group discussions, is a novel smartphone app that uses GPS to identify the user's location to record location coordinates meet two primary functions: (1) to allow the participant to locate ART facilities in South Africa that are near her current location, and (2) to trace mobility prospectively. We employ an algorithm on the mobile application to reliably determine when a participant has traveled outside the study area. If the participant travels more than 50 km outside the study area for more than 7 days, the app will automatically notify the participant of available care facilities near her new location, and will provide the facility address and phone number, if available. The notifications will be available to both English and isiXhosa-language speakers (the predominant languages of the region).

Through the TN CFAR award, we conducted a proof-of-concept study by enrolling four participants at the proposed study site and following them for 90 days (Vanderbilt IRB approval: 170510; UCT HREC: 227/2017; ClinicalTrials.gov: 170510). We identified technological issues to address in order to

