Mobility data will be collected throughout the follow-up period. Geospatial coordinates will be recorded with a timestamp. Upon bulk extraction of these data, we will import location information as decimal degree coordinates into ArcMap spatial analysis software. Data charges related to the app are reverse-billed through our app development consultants to ensure timely transmission of data with no cost to participants.

Weekly raffle incentive

To encourage participants to keep the CareConekta app installed on their phone and the GPS function enabled throughout the entire study period, we will offer an incentive: a weekly raffle of one 200MB data bundle (worth approximately \$4). Participants will be eligible to enter the raffle if their phone sent GPS coordinates at least once per day for the prior week. Winners will be randomly selected among all eligible participants using a randomization code automated in STATA. The weekly raffle incentive will only apply to participants enrolled from October 2020 onwards and who have signed version 5.0 or later of the Informed Consent document. There is no limit to the number of times a participant may win the raffle.

Six-month postpartum follow-up visit procedures

Recontacting participant

All participants will be recontacted six months postpartum to return to the study site for a one-time visit. A minimum of three contact attempts by phone and/or home visit will be made for each participant. All contact attempts (successful or not) will be recorded on a contact log.

Follow-up questionnaire

Study staff will complete a face-to-face questionnaire with each participant. This follow-up questionnaire will include reasons for overall acceptability of CareConekta (standard or enhanced), reasons for travel and clinic switching, and barriers and facilitators to care since the start of the study. Response options primarily will be categorical, with open-ended questions to allow for deeper elaboration. Additional questions will be asked of participants in the intervention arm regarding acceptability and feasibility of the intervention. Responses will be recorded directly into a REDCap database by an interviewer using a tablet computer or laptop. This questionnaire may be conducted telephonically.

Viral load testing and potential blood draw

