In routine care in this setting, viral load tests are to be repeated every three months in pregnancy and every six months during breastfeeding, so we expect that most women will have a routine viral load completed before six months postpartum. To avoid additional blood draws for the participant, at the follow-up visit, the study staff will check NHLS to determine the most recent viral load test. If the participant has had no viral load test within 3 months prior to the six-month study follow-up visit, a blood draw for viral load will be conducted by the clinical staff at the Gugulethu CHC. A clinic nurse will collect 5 ml of venous blood, which will be transported daily to the National Health Laboratory Services (NHLs) for HIV viral load testing (Abbott Molecular RealTime HIV-1 assay (Abbott Molecular, Illinois, USA). We will not recontact participants about viral load results unless participants are on ART and the viral load result indicates lack of viral suppression. In that case, results will be made available to participants over the phone (or in person, at participant's wish) with appropriate referrals. For all participants, viral load results will be captured using the participants provincial folder number into the NHLs database, as is standard practice for routine laboratory results in South Africa.

Uninstall app

During the follow-up visit, the CareConekta app will be uninstalled from each participant's phone.

Reimbursement

After all the above steps are complete, the enrollment visit will conclude with providing the participant R150 reimbursement for transport and missed opportunity costs. Payment will be made in cash and/or grocery vouchers and will be recorded in a reimbursement log.

File review activities

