Electronic and paper files will be reviewed after the participant's final visit to assess engagement in HIV care. If the participant fails to return for a final visit, files will be reviewed a minimum of seven months after estimated delivery. Electronic data on health facility visits and pharmacy dispensing, including facility recorded deaths, will be requested the Provincial Health Data Centre of the Western Cape Department of Health by providing a list of folder numbers of women who have consented and enrolled in the study. These data include all public health facilities in the Western Cape Province, which is the location of the study site. Laboratory records, including viral loads, from any South African facility will be abstracted from the NHLS database. Participants in both arms who are lost from the study at the time of study close will be traced through staff outreach and electronic/paper medical records. Informed consent will include permission to link with electronic medical records.

Table of schedule of measures

Item for completion	Enrolment	Early postpartum phone call	6 months postpartum
Eligibility Checklist	x		
Informed Consent	x		
Linkage form	x	x child details	
Randomisation log	x		
Demographics and medical history	x		x
Maternal mobility (past and planned)	x		x
Maternal clinic switching	x		x
Perceived barriers and facilitators of engagement in care	x		x
Depression (PHQ-4)	x		x
Alcohol and drug use (AUDIT-C and DUDIT Q1)	x		x
Patient provider relationship scale	x		x
ART adherence	x		x
WHO VAW (intimate partner violence)	x		
Social impact scale (stigma)	x		
Availability of social support	x		
Life events (trauma)			x
Infant health			x
Child mobility			x
Acceptability of CareConekta			x
Impact of COVID-19 & lockdown of HIV care and mobility			x
Laboratory tests			
HIV viral load*			x
Record review			
Antenatal and obstetric information	x	x	x
ART pharmacy records	x	x	x
Maternal laboratory results	x	x	x
Child HIV testing		x	x

* If no routine viral load result found in the three months before the study visit

DATA COLLECTION AND STORAGE

Data collection methods

Data will be collected in three ways:

- Face-to-face enrollment and follow-up questionnaires

- Medical record review (electronic and paper file records) to determine participant engagement in HIV care
- Electronic app usage and mobility data

Questionnaire data

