The PI will monitor the study safety data on an ongoing basis. They will report to their IRBs and the South Africa HREC any breaches in confidentiality identified. In the event that a breach in confidentiality does occur, staff will be retrained on human subjects' protection and confidentiality if possible or removed from subject contact if the either the breach is too serious or if the PIs feel the staff member cannot be sufficiently retrained. Staff will be made aware of this condition on employment.

The PI will be responsible for reporting to the grant program director any action resulting in a temporary or permanent suspension of the research.

We will not convene a Data Safety Monitoring Board (DSMB) for this study.

Data accuracy and completeness

In addition to the co-investigators, the local South African study team will consist of a study coordinator, a site coordinator, and an interviewer/fieldworker. These team members will be trained in human subjects' research through the NIH's website or through a presentation developed by UCT faculty based on the NIH course, but adapted to the local context. Prior to contact with any subjects, all staff with participant interaction duties will be trained on the background and objectives of the study, procedures for obtaining informed consent, and correct administration of the questionnaire. Training will include procedures for minimizing risk to subjects, assuring data accuracy and protocol

compliance. The study team will also be asked to complete several practice interviews. To avoid bias and/or contamination, the study staff member who conducts interviews will not deliver the intervention calls and/or messages.

Participant remuneration

Following standards set by the University of Cape Town Research Ethics Committee, all participants will be reimbursed R150 (approximately US \$10.50) per study visit (enrollment and follow-up) for transport and missed opportunity costs. There will be no participant reimbursement for routine care visits made between study visits.

REFERENCES

1. Statistics South Africa. *Mid-Year Population Estimates 2018*. Pretoria; 2018. <https://www.statssa.gov.za/publications/P0302/P03022018.pdf>.
2. UNAIDS. *Global Report: UNAIDS Report on the Global AIDS Epidemic 2013*. Geneva; 2013. http://www.unaids.org/en/media/unaids/contentassets/documents/epidemiology/2013/gr2013/UNAIDS_Global_Report_2013_en.pdf.

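### Women who are away and out of care at six months are the least likely to have a current viral load, and the plan sets neither a window for the result nor a rule for women without one

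*Combined protocol and SAP*

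**What the plan says.** Under Six-month postpartum follow-up visit procedures: "All participants will be recontacted six months postpartum to return to the study site for a one-time visit". Of the questionnaire the same section adds: "This questionnaire may be conducted telephonically". No remote option is given for blood.

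Under Viral load testing and potential blood draw, the study sample depends on the recent record: "If the participant has had no viral load test within 3 months prior to the six-month study follow-up visit", then "a blood draw for viral load will be conducted by the clinical staff at the Gugulethu CHC". The same section says of routine care that "viral load tests are to be repeated every three months in pregnancy and every six months during breastfeeding", and expects most women to have had a routine test before six months postpartum.

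Under File review activities: "Laboratory records, including viral loads, from any South African facility will be abstracted from the NHLS database". Visit and pharmacy data, by contrast, come from public facilities in the Western Cape only. Women lost at study close are traced in both arms through outreach and records.

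Under Participant remuneration, every woman receives R150 "per study visit (enrollment and follow-up) for transport and missed opportunity costs", with no element for distance. The Study site section expects births at this unit to involve women from another province, "resulting in travel to and from the Eastern Cape during pregnancy and postpartum".

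In the analysis plan, Aim 1b (control arm only) and Aim 2b (both arms) each report suppression six months after delivery at two thresholds, with Cox models and Kaplan-Meier curves. Aim 2b takes the test nearest to six months. Aim 1b does not say which test counts. Neither sets a window or says what happens to a woman with no result.

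**The concern.** Whether a woman has a current viral load depends on where she is and whether she is in care. A woman at home can be bled at the visit. A woman who is away but attending a clinic elsewhere in South Africa may have a routine result in the national laboratory database. A woman who is away and out of care has neither, unless she travels back. She is also the woman least likely to be suppressed. Missingness is therefore tied to the Aim 1b exposure and to the outcome together.

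If the analysis uses measured women only, the travellers who remain are mainly those who returned or found care, and mobility looks less harmful than it is. If an antenatal or early postpartum result may stand in as the nearest test, a woman who has since left care is counted by her in-care value. Aim 1b is most exposed, because mobility is the comparison itself. In Aim 2b, the intervention is meant to connect travelling women to local clinics, so it may also change who has a result. The protocol says the pilot will inform the sample sizes of larger studies, so a distorted estimate would carry forward.

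**Working it through.** **The plan's own figure.** The Sample Size section expects 25% to travel: 0.25 × 200 = 50 women, as stated. With 1:1 allocation that is about 25 per arm. How many are still away at six months is not given. If 20% to 60% are (assumed), that is 10 to 30 women.

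**Inputs.**
- Out of care among travellers: control 47.9%, borrowed from the earlier Johannesburg cohort in the Introduction; intervention 25% (assumed).
- Suppressed: 90% in care, 30% out of care (assumed).
- In-care travellers with a result: 90% (assumed).
- Out-of-care travellers with a result: m, varied from 10% to 90%.
- Non-travellers: 15% out of care; 95% of in-care and 80% of out-of-care women measured (assumed).

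**Formulas**, with o the out-of-care share:
- True suppression = (1−o)×0.9 + o×0.3
- Measured share M = (1−o)×0.9 + o×m
- Measured and suppressed S = (1−o)×0.9×0.9 + o×m×0.3
- Measured-only estimate = S/M; all unmeasured unsuppressed = S; all unmeasured suppressed = S + 1 − M

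**Aim 1b (control arm).** True suppression in travellers: 0.521×0.9 + 0.479×0.3 = 61.3%. In non-travellers: 0.85×0.9 + 0.15×0.3 = 81.0%. The true gap is 19.7 points. Measured-only, non-travellers read 82.2%.

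| m | Travellers, measured-only | Gap to non-travellers |
|---|---|---|
| 10% | 84.4% | −2.2 |
| 30% | 75.9% | 6.3 |
| 60% | 67.2% | 15.0 |
| 90% | 61.3% | 21.0 |

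At m = 30%, S = 0.422 + 0.043 = 0.465 and M = 0.469 + 0.144 = 0.613. The bounds for control travellers are then 46.5% and 0.465 + 0.387 = 85.3%, which contain the true 61.3%.

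Suppose instead that an older in-care result fills every gap. At m = 30% control travellers read 0.469 + 0.479×(0.3×0.3 + 0.7×0.9) = 81.4%. Non-travellers read 0.765 + 0.15×(0.8×0.3 + 0.2×0.9) = 82.8%. The gap is 1.4 points.

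**Aim 2b, travellers only.** True: 61.3% v 75.0%, a difference of 13.7 points. At m = 30% in both arms:

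| Handling of women without a result | Control | Intervention | Difference |
|---|---|---|---|
| Measured only | 75.9% | 84.0% | 8.1 |
| Old in-care result used | 81.4% | 85.5% | 4.1 |
| All unmeasured unsuppressed | 46.5% | 63.0% | 16.5 |
| All unmeasured suppressed | 85.3% | 88.0% | 2.7 |

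Unequal measurement can also create a difference. With no true effect (47.9% out of care in both arms), measuring 60% of out-of-care control travellers but 30% in the intervention arm gives +8.7 points measured-only; the reverse gives −8.7.

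**A second set of assumptions**, for women away at six months: 30% v 60% linked locally and always measured; 80% suppressed if linked, 30% if not; 20% of the unlinked attend. True: 45% v 60% (15 points). Measured-only: 0.282/0.44 = 64.1% v 0.504/0.68 = 74.1% (10 points). Unmeasured as unsuppressed: 28.2% v 50.4% (22 points). Unmeasured as suppressed: 84.2% v 82.4% (−2 points).

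**Whole arms.** In the first model a true 3.4 points reads 1.5 measured-only. In the second, take 15 women away per arm and the other 85 at 85% suppressed, all measured. The true difference is 0.15 × 15 = 2.25 points. Measured-only gives (72.25 + 7.56)/95.2 − (72.25 + 4.23)/91.6 = 83.8% − 83.5%, about 0.3. The shift is about 1.9 points each time. For scale, the 95% half-width with 100 per arm near 80% is 1.96 × √(2 × 0.8 × 0.2/100) = 11 points.

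**The case against.** The mitigations are real. Laboratory capture is national, at least three contacts by telephone and/or home visit are planned, and lost women in both arms are traced. Most women should have some viral load on file, because all enrol in antenatal care and routine testing continues. This narrows the gap to women with no recent test who do not return. It does not close it: none of these routes describes a sample taken away from Gugulethu, and the database holds only tests that were done. An earlier result prevents missingness only by substituting a value from when the woman was in care.

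The three-month look-back might be read as an implied window. It decides who is bled at the visit. The analysis sections do not carry it over as the rule for which result counts.

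The planned analysis is a Cox model, whereas the arithmetic above uses proportions. That is fair, and the figures do not translate into hazard ratios. A Cox model still needs a censoring rule for women with no result, and none is stated.

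A reader might infer three stronger points that the documents do not support:
- **That the flat R150 causes the problem.** No travel cost or attendance rate is given, the amount follows a university ethics committee's standard, and nothing shows that money is the binding barrier.
- **That an intervention effect is hidden.** This requires a measured-only or old-result analysis with similar measurement in both arms. Counting unmeasured women as unsuppressed enlarges the difference on the same inputs.
- **That an unlinked control woman has no viral load at all.** She may have an antenatal result, and the Aim 2b rule would let it count.

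Finally, the protocol already says that Aim 2b is not powered, and a shift of about 2 points is small beside an 11-point half-width. That stands, and it is why the point bears mainly on Aim 1b.

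**Conclusion.** The concern holds for outcome measurement and its analysis. One study draw site, laboratory records that show only tests done, no window and no missing-result rule together leave women who are away and out of care as those least likely to have a current viral load. In Aim 1b a measured-only or old-result analysis would understate the association with mobility. On the stated assumptions a true 19.7-point gap reads 6.3 points when 30% of out-of-care travellers are measured, and 15.0 when 60% are. In Aim 2b the direction is not fixed, and the whole-arm shift is about 2 points.

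Apart from the 25% who travel and the borrowed 47.9%, the inputs are assumed. The sizes are illustrations; the direction in Aim 1b follows from out-of-care travellers being both less often measured and less often suppressed. This is an inexpensive improvement that affects what Aim 1b can conclude. It does not undermine the trial.

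**What to change.** In the analysis plan, Aims 1b and 2b:

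1. Set a window around six months postpartum for the viral load that counts, and use it in both aims. Define it from the delivery date so that it also applies to women with no visit. Routine testing while breastfeeding is six-monthly, so a short look-back will leave some in-care women unmeasured; a wider window can be a sensitivity analysis.
2. Report the share of women with a result in the window by arm and by home or away status at six months, using the GPS and questionnaire data already planned.
3. Beside the measured-only estimate, give both bounds: all unmeasured women unsuppressed, and all unmeasured women suppressed. The first alone can inflate the intervention effect. The bounds hold for each group's proportion; a difference computed under one common rule is not a guaranteed limit.
4. State how women without a result enter the Cox models, including when they are censored.
5. Do not treat absence of care contact in the visit and pharmacy data as proof of being out of care for women who are away. Those data cover the Western Cape only, so a traveller in care elsewhere can look lost.

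The cost is a short amendment to the analysis text, a little more analysis, and wider, less favourable ranges. Distance-related transport reimbursement and payment for telephone interviews are optional points to raise with the ethics committee; the case for the five steps does not depend on them.
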